## 9.2 Responsibility for Analyses/In-house Blinding

The statistical analysis of the data obtained from this study will be the responsibility of the Clinical Biostatistics department of the Sponsor.

The Sponsor will generate the randomized allocation schedule(s) for study intervention assignment for this protocol, and the randomization will be implemented in interactive voice response system.

This study will be conducted as a double-blind study under in-house blinding procedures. The official, final database will not be unblinded until medical/scientific review has been performed, protocol deviations have been identified, and data have been declared final and complete.

Blinding procedures related to the planned IAs are described in Section 9.7.

## 9.3 Hypotheses/Estimation

Objectives and hypotheses of the study are stated in Section 3.

## 9.4 Analysis Endpoints

### 9.4.1 Efficacy Endpoints

Dual Primary

Progression-free Survival (PFS) per RECIST 1.1 Assessed by BICR

PFS is defined as the time from randomization to the first documented disease progression per RECIST 1.1 based on BICR or death due to any cause, whichever occurs first. See Section 9.6.1 for the censoring rules.

Overall Survival (OS)

Overall survival is defined as the time from randomization to death due to any cause. Participants without documented death at the time of analysis will be censored at the date of last known contact.

## Secondary

### Objective Response Rate (ORR) per RECIST 1.1 Assessed by BICR

Objective response rate is defined as the proportion of participants who have a CR, or a PR. Responses are based on confirmed assessments by the BICR per RECIST 1.1.

### Duration of Response (DOR) per RECIST 1.1 Assessed by BICR

For participants who demonstrate CR or PR, DOR is defined as the time from first documented evidence of CR or PR until disease progression or death. Response duration for participants who have not progressed or died at the time of analysis will be censored at the date of their last tumor assessment. Response duration will be calculated per RECIST 1.1 based on BICR by the imaging vendor.

Additional details of the efficacy measurements are described in Section 4.2.1.1.

## **9.4.2 Safety Endpoints**

Safety parameters are described in Section 4.2.1.2.

Safety and tolerability will be assessed by clinical review of all relevant parameters including AEs, laboratory values and vital signs.

## **9.4.3 Patient-reported Outcome Endpoints**

The following secondary PRO endpoints will be evaluated:

- Global Health Status/QoL scale (EORTC QLQ-C30 items 29-30)
- Physical functioning scale (EORTC QLQ-C30 items 1-5)

The EQ-5D-5L will be evaluated as an exploratory endpoint. The EQ-5D-5L analyses will be described in the sSAP.

## **9.5 Analysis Populations**

### **9.5.1 Efficacy Analysis Population**

The ITT population will serve as the population for primary efficacy analysis (PFS and OS). All randomized participants will be included in this population. Participants will be included in the treatment group to which they are randomized.

The global study will only contain approximately 660 randomized participants. The extension portion of the study enrolling additional China participants will not be included in the global study population used as the primary population to address protocol objectives but will be analyzed as specified in the sSAP.

### **9.5.2 Safety Analysis Population**

The APaT population will be used for the analysis of safety data in this study. The APaT population consists of all randomized participants who received at least one dose of study intervention. Participants will be included in the treatment group corresponding to the study intervention they actually received for the analysis of safety data using the APaT population. For most participants this will be the treatment group to which they are randomized.

Participants who take incorrect study intervention for the entire treatment period will be included in the treatment group corresponding to the study intervention actually received. Any participant who receives the incorrect study medication for 1 or more cycles but receives the correct treatment for the remaining cycles will be analyzed according to the participant's randomized treatment group and a narrative will be provided for any events that occur during the cycle for which the participant was incorrectly dosed.

At least 1 laboratory or vital sign measurement obtained subsequent to at least 1 dose of study intervention is required for inclusion in the analysis of each specific parameter. To assess change from baseline, a baseline measurement is also required.

The global study will only contain approximately 660 randomized participants. The extension portion of the study enrolling additional China participants will not be included in the global study population used as the primary population to address protocol objectives but will be analyzed as specified in the sSAP.

### **9.5.3 Patient-reported Outcome Analysis Populations**

The PRO analyses are based on the PRO Full Analysis Set population, defined as participants who have at least 1 PRO assessment available and have received at least 1 dose of study medication.

### **9.5.4 Pharmacokinetic Analysis Population**

The Population PK Analysis Set includes all the participants who have received at least 1 dose of study intervention with documented dosing history in the lenvatinib plus pembrolizumab arm and have measurable plasma levels of lenvatinib or serum levels of pembrolizumab.

## **9.6 Statistical Methods**

NOTE: As of Amendment 07, the prespecified final analysis of the study described in the SAP will not be performed. Safety analysis will be performed at the end of the study; there will be no further analyses of efficacy and ePRO endpoints. Original protocol text that is contained in this section has been retained for reference.

This section describes the statistical methods that address the primary and secondary objectives. Methods related to the exploratory objectives will be described in the sSAP.

The stratification factors used for randomization (Section 6.3.2) will be applied to the models for efficacy described herein. If there are a small number of responses in one or more strata,

for the purpose of analysis, strata will be combined to ensure a sufficient number of participants, responses, and events in each stratum. Details regarding the combining of strata will be specified in the sSAP prior to database lock based on a blinded review of response and event counts by stratum.

### 9.6.1 Statistical Methods for Efficacy Analyses

[figure not shown]
#### 9.6.1.1 Progression-free Survival

The nonparametric Kaplan-Meier method will be used to estimate the PFS curve in each treatment group. CCI [REDACTED]

[figure not shown]
[REDACTED]. The stratification factors used for randomization (see Section 6.3) will be applied to both the stratified log-rank test and the stratified Cox model.

Since disease progression is assessed periodically, PD can occur any time in the time interval between the last assessment where PD was not documented and the assessment when PD is documented. The true date of disease progression will be approximated by the date of the first assessment at which PD is objectively documented per RECIST 1.1 by BICR. Death is always considered as a confirmed PD event. Participants who do not experience a PFS event will be censored at the last disease assessment. Sensitivity analyses will be performed for comparison of PFS based on investigator's assessment.

CCI

CCI

### 9.6.1.2 Overall Survival

The nonparametric Kaplan-Meier method will be used to estimate the survival curves. CCI

The stratification factors used for randomization (see Section 6.3.2) will be applied to both the stratified log-rank test and the stratified Cox model if applicable.

Participants without documented death at the time of analysis will be censored at the date of last contact.

### 9.6.1.3 Objective Response Rate

The stratified Miettinen and Nurminen method will be used for the comparison of the ORR between the 2 treatment groups. CCI

. The stratification factors used for randomization (Section 6.3) will be applied to the analysis.

[figure not shown]
CCI

If sample size permits, DOR will be summarized descriptively using Kaplan-Meier medians and quartiles. Only the subset of participants who show a confirmed CR or PR will be included in this analysis. The details of censoring rules for DOR analysis will be described in the sSAP.

### 9.6.1.4 Analysis Strategy for Key Efficacy Endpoints

CCI

CCI

[figure not shown]
## 9.6.2 Statistical Methods for Safety Analyses

Safety and tolerability will be assessed by clinical review of all relevant parameters including AEs, laboratory tests and vital signs.

[figure not shown]
### Adverse Events

Adverse events will be coded using the standard Medical Dictionary for Regulatory Activities (MedDRA) and grouped system organ class. AEs will be graded by the investigator according to the NCI CTCAE, v4.0.

CCI

CCI

[figure not shown]

### 9.6.3 Analysis Methods for Patient-reported Outcome Endpoints

The change from baseline in the following secondary PRO endpoints from the EORTC QLQ C30 will be assessed:

- Global health status/QoL score (QLQ-C30 items 29-30)
- Physical functioning score (QLQ-C30 items 1-5)

CCI

A large black rectangular redaction box covers the majority of the page content below the CCI label, starting from the list of endpoints and extending down to the section header for 9.6.4.

### 9.6.4 Summaries of Demographic and Baseline Characteristics

The comparability of the treatment groups for each relevant demographic and baseline characteristic will be assessed by the use of tables and/or graphs. No statistical hypothesis tests will be performed on these characteristics. The number and percentage of participants screened and randomized and the primary reasons for Screening failure and discontinuation will be displayed. Demographic variables (eg, age), baseline characteristics, primary and secondary diagnoses, and prior and concomitant therapies will be summarized by treatment either by descriptive statistics or categorical tables.

### 9.7 Interim Analyses

NOTE: As of Amendment 07, the prespecified final analysis of the study described in the SAP will not be performed. This section is retained for reference.

An eDMC will be convened to review the unblinded efficacy results and accumulating safety at the planned IAs. An external unblinded statistician and programmer will be responsible for conducting and presenting the IAs results to the eDMC. The eDMC responsibilities and review schedules will be outlined in the eDMC charter. The recommendation of the eDMC will be communicated to an Executive Oversight Committee. In the event of a recommendation to halt the study early due to safety concerns, the Sponsor will communicate

[figure not shown]
this to the appropriate regulatory agencies. If the eDMC recommends modifications to the design of the protocol or discontinuation of the study, this Executive Oversight Committee may be unblinded to results at the treatment level in order to act on these recommendations.

A limited number of additional personnel may be unblinded, if required, in order to act on the recommendations of the eDMC. The extent to which individuals are unblinded to the results will be documented. Additional logistical details, revisions to the above plan and data monitoring guidance will be provided in the eDMC Charter.

If the eDMC makes a recommendation to alter the study conduct, it may be implemented upon EOCs advice; and health authorities and IRB/IEC will be informed accordingly.

#### **9.7.1 Efficacy Interim Analyses**

CC1

[figure not shown]
### 9.7.2 Safety Interim Analyses

The eDMC conducted regular safety interim analyses. The timing of these safety interim analyses was specified in the eDMC charter. No further formal efficacy analysis will be conducted. Safety monitoring will continue as per protocol.

[figure not shown]
### 9.8 Multiplicity

NOTE: As of Amendment 07, the prespecified final analysis of the study described in the SAP will not be performed. Original protocol text that is contained in this section has been retained for reference.

CCI

[figure not shown]

CCI

[figure not shown]

### 9.8.1 Progression-free Survival

[figure not shown]
CCI

[figure not shown]
CCI

[figure not shown]
CCI

### 9.8.2 Overall Survival

CCI

CCI

### 9.8.3     Objective Response Rate

CCI

#### 9.8.4 Safety Analyses

[figure not shown]
The eDMC has responsibility for assessment of overall risk/benefit. When prompted by safety concerns, the eDMC can request corresponding efficacy data. External DMC review of efficacy data to assess the overall risk/benefit to study participants will not require a multiplicity adjustment typically associated with a planned interim efficacy analysis; however, to account for any multiplicity concerns raised by the eDMC review of unplanned efficacy data prompted by safety concerns, a sensitivity analysis for PFS adopting a conservative multiplicity adjustment will be prespecified in the sSAP. This analysis will be performed if efficacy data is requested by the eDMC during a safety evaluation to assess risk/benefit.

### 9.9 Sample Size and Power Calculations

NOTE: As of Amendment 07, the prespecified final analysis of the study described in the SAP will not be performed. This section is retained for reference.

A total of approximately 660 participants will be randomized in a 1:1 ratio in the global study.

[figure not shown]
CCI

#### 9.9.1 Progression-free Survival

PFS is a dual primary endpoint. CCI

CCI

[figure not shown]
#### 9.9.2 Overall Survival

Overall survival is a dual primary endpoint. CCI

CCI

[figure not shown]

CCI

### 9.9.3 Objective Response Rate

[figure not shown]
ORR is a secondary endpoint. CCI

[figure not shown]
## 9.10 Subgroup Analyses

Both efficacy and safety may be analyzed for the following subgroups as appropriate. For efficacy endpoints, the HR and two-sided 95% CI for comparing PFS as assessed by BICR and OS of combination therapy versus pembrolizumab monotherapy will be presented in forest plots for the subgroups. Median PFS and 95% CIs will be presented for all subgroups. Similar plots will be provided for OS. For safety endpoints, all treatment-emergent AEs, treatment-emergent AEs of NCI CTCAE v4.0 Grades 3 and 4, and treatment-emergent SAEs may be summarized by the subgroups.

CCI

CCI

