#### **8.4.6 Disease-related Events and/or Disease-related Outcomes Not Qualifying as AEs or SAEs**

Efficacy endpoints as outlined in this section will not be reported to the Sponsor as described in Section 8.4.1.

Specifically, the suspected/actual events covered in this exception include any event that is disease progression of the cancer under study.

The Sponsor will ensure that unblinded aggregated efficacy endpoint events and safety data are monitored to safeguard the participants in the study.

Any suspected endpoint which upon review is not progression of the cancer under study will be forwarded to Global Pharmacovigilance as an SAE within 24 hours of determination that the event is not progression of the cancer under study.

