## 9 STATISTICAL ANALYSIS PLAN

### As of Amendment 07: The Statistical Analysis Plan is amended as follows.

NOTE: Based on the data from an interim safety and efficacy analysis for LEAP-003 (data cutoff 18-JAN-2023), eDMC recommended stopping the study due to lack of efficacy because pembrolizumab in combination with lenvatinib did not demonstrate an improvement in OS, one of the trial's dual primary endpoints, compared to pembrolizumab plus placebo and appears unlikely to do so in a future analysis. Based upon these data and the recommendation of the eDMC, the study was unblinded as of 27-MAR-2023. The prespecified final analysis of the study described in the SAP will not be performed. Safety analysis will be performed at the end of the study; there will be no further analyses for efficacy and ePRO endpoints.

This section outlines the statistical analysis strategy and procedures for the study. The study has been unblinded as of 27-MAR-2023. Changes made to primary and/or key secondary hypotheses, or the statistical methods related to those hypotheses that occurred prior to Amendment 07 were documented in previous protocol amendments(s) (consistent with International Conference on Harmonisation [ICH] Guideline E-9). Changes to exploratory or other nonconfirmatory analyses made after the protocol has been finalized will be documented in an sSAP and referenced in the Clinical Study Report for the study. Post hoc exploratory analyses will be clearly identified in the Clinical Study Report. Separate analysis plans (ie, separate documents from the sSAP) may be developed to detail other planned analyses.

The extension portion of the study, which includes the additional enrollment of Chinese participants, will not be included as part of the study population used to address the protocol objectives. Additional detail regarding the analysis associated with these participants will be described in the sSAP.

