**An SAE is defined as any untoward medical occurrence that, at any dose:**

- a. Results in death
- b. Is life-threatening
  - The term “life-threatening” in the definition of “serious” refers to an event in which the participant was at risk of death at the time of the event. It does not refer to an event, which hypothetically might have caused death, if it were more severe.

- c. Requires inpatient hospitalization or prolongation of existing hospitalization
  - Hospitalization is defined as an inpatient admission, regardless of length of stay, even if the hospitalization is a precautionary measure for continued observation. (Note: Hospitalization for an elective procedure to treat a preexisting condition that has not worsened is not an SAE.) A preexisting condition is a clinical condition that is diagnosed prior to the use of an MSD product and is documented in the participant's medical history.
- d. Results in persistent or significant disability/incapacity
  - The term disability means a substantial disruption of a person's ability to conduct normal life functions.
  - This definition is not intended to include experiences of relatively minor medical significance such as uncomplicated headache, nausea, vomiting, diarrhea, influenza, and accidental trauma (eg, sprained ankle) that may interfere with or prevent everyday life functions but do not constitute a substantial disruption.
- e. Is a congenital anomaly/birth defect
  - In offspring of participant taking the product regardless of time to diagnosis.
- f. Other important medical events
  - Medical or scientific judgment should be exercised in deciding whether SAE reporting is appropriate in other situations such as important medical events that may not be immediately life-threatening or result in death or hospitalization but may jeopardize the participant or may require medical or surgical intervention to prevent 1 of the other outcomes listed in the above definition. These events should usually be considered serious.
  - Examples of such events include invasive or malignant cancers, intensive treatment in an emergency room or at home for allergic bronchospasm, blood dyscrasias, or convulsions that do not result in hospitalization, or development of drug dependency or drug abuse.

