#### Assessment of intensity/toxicity

- An event is defined as “serious” when it meets at least 1 of the predefined outcomes as described in the definition of an SAE, not when it is rated as severe.
- The investigator will make an assessment of intensity for each AE and SAE (and other reportable safety event) according to the NCI CTCAE, version 4.0. Any AE that changes CTCAE grade over the course of a given episode will have each change of grade recorded on the AE CRFs/worksheets.
  - Grade 1: Mild; asymptomatic or mild symptoms; clinical or diagnostic observations only; intervention not indicated.
  - Grade 2: Moderate; minimal, local, or noninvasive intervention indicated; limiting age-appropriate instrumental ADL.
  - Grade 3: Severe or medically significant but not immediately life-threatening; hospitalization or prolongation of hospitalization indicated; disabling; limiting self-care ADL.
  - Grade 4: Life-threatening consequences; urgent intervention indicated.
  - Grade 5: Death related to AE.

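### The severe-grade category for subgroup safety summaries stops at Grade 4, so it can omit participants with fatal AEs to an extent that depends on an unstated counting rule

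*Combined protocol and SAP*

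**What the plan says.** Section 9.10 opens its safety sentence with all treatment-emergent AEs and continues: "treatment-emergent AEs of NCI CTCAE v4.0 Grades 3 and 4, and treatment-emergent SAEs may be summarized by the subgroups". All three summaries are optional, by subgroup.

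The grading scale in Appendix 3 (Section 10.3.5, assessment of intensity/toxicity) goes one step further: "Grade 5: Death related to AE". The same list governs how grade changes are captured: "Any AE that changes CTCAE grade over the course of a given episode will have each change of grade recorded on the AE CRFs/worksheets".

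Section 10.3.3 makes any fatal AE serious, since its first criterion is "Results in death". Section 8.4.6 takes deaths from the melanoma itself out of AE reporting: "the suspected/actual events covered in this exception include any event that is disease progression of the cancer under study".

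The safety analysis is still to come. The note that opens Section 9 states: "Safety analysis will be performed at the end of the study; there will be no further analyses for efficacy and ePRO endpoints". Sections 9.6 to 9.9 each carry a note that text is kept for reference; Section 9.10 carries none.

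**The concern.** Readers commonly take a Grade 3 and 4 row as the rate of severe toxicity. A category that ends at Grade 4 is not monotone in severity: under maximum-grade counting, a participant whose Grade 4 event becomes fatal leaves the category and the severe-AE proportion falls. Because progression of the melanoma is excepted from AE reporting, the Grade 5 AEs are essentially non-progression deaths, which are the deaths most relevant to toxicity.

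At stake is the reading of one descriptive row in each subgroup table. If fatal AEs were more frequent on one arm, that arm's severe-AE proportion would be understated by more. The point carries some weight because safety is the only global analysis still planned.

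**Working it through.** The plan states no figure to reproduce, so the check compares definitions and then bounds the effect.

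**Where a treatment-emergent fatal AE is counted in Section 9.10**

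- All treatment-emergent AEs: counted, since no grade limit applies.
- Treatment-emergent SAEs: counted, since death is a seriousness criterion in Section 10.3.3.
- Grade 3 and 4 AEs: the Grade 5 record itself is not counted.

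**What happens to the participant in the Grade 3 and 4 row**

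In one arm, let N be the number treated, F the number with a Grade 5 AE, and M the number of those F who have no Grade 3 or 4 record of any kind. Then 0 ≤ M ≤ F.

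- Maximum-grade counting: omitted = F, so the proportion is low by F/N.
- Any-event counting: omitted = M, so the proportion is low by M/N. Appendix 3 has every grade change recorded, so a fatal episode that passed through Grade 3 or 4 keeps the participant in the row, as does any other Grade 3 or 4 AE. M can be 0.

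The visible text of Section 9.10 states neither rule. The understatement is therefore between 0 and F/N.

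**Size within an arm**

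- Section 9.9: "A total of approximately 660 participants will be randomized in a 1:1 ratio in the global study". So N is about 660 / 2 = 330, assuming nearly all randomized participants were treated.
- The documents give no fatal-AE rate for this trial. Assumed range: 1% to 5%.
- Upper bound on omissions: 330 × 0.01 = 3.3 and 330 × 0.05 = 16.5, or about 3 to 17 participants per arm over all levels of a subgroup factor.
- Lower bound: 0.
- One level of a subgroup is smaller. With an assumed 30 participants, one omission is 1/30 = 3.3 percentage points. The subgroup list is redacted, so 30 is only an illustration.

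**Size in a treatment comparison**

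Write A for the combination arm and B for the control arm. The A minus B difference in the Grade 3 and 4 proportion equals the difference in the Grade 3 to 5 proportion minus (omitted A / N A − omitted B / N B). Under maximum-grade counting, equal fatal-AE rates give a shift of 0. The two ends of the assumed range, 5% on one arm and 1% on the other, give 5 − 1 = 4 percentage points. The documents do not say which arm, if either, would have more.

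**With Grades 3 to 5**

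A participant has some record of Grade 3 or higher exactly when the maximum grade is 3 or higher. The count is then the same under both rules, and no fatal case is omitted.

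**The case against.** Four objections have force.

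1. A reader might infer that the subgroup tables count only Grade 3 and 4 AEs, so that deaths vanish from them. They do not. The same sentence of Section 9.10 adds all AEs and SAEs, and every treatment-emergent fatal AE is in both. What remains is that neither summary separates fatal events from the rest, and neither corrects the Grade 3 and 4 proportion.

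2. A reader might infer that a participant whose worst event is fatal must drop out of the severe-AE count. That follows only under maximum-grade counting, which is not specified. Under any-event counting the loss could be nil. This stands, and it is why the size is a range starting at zero.

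3. The AE methods in Section 9.6.2 are largely redacted, as is the subgroup detail after the quoted sentence, and the supplemental SAP is not among the documents. Fatal AEs may have their own line there, and the counting rule may be stated there. The documents therefore do not support a claim that the plan as a whole fails to tabulate deaths.

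4. The summaries are optional and descriptive, and the visible text attaches no test or decision rule to them. This stands too and keeps the point minor.

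The objections leave intact the visible and complete wording of Section 9.10, which excludes the protocol's highest AE grade from its severe-grade category.

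**Conclusion.** The point holds as a minor defect in a category definition. The Grade 3 and 4 row in the optional subgroup summaries understates the share of participants with a Grade 3 or higher AE by between zero and the fatal-AE rate. The upper bound of about 3 to 17 participants per arm rests on an assumed fatal-AE rate of 1% to 5% and about 330 treated per arm; it is reached only if counting is by maximum grade.

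A reader might go further and conclude that subgroup safety comparisons are biased in the reassuring direction. The documents do not support that: the shift in a comparison is the between-arm difference in omitted participants, its direction is unknown, and the SAE summary listed alongside includes the deaths.

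**What to change.** In Section 9.10, replace Grades 3 and 4 with Grades 3 to 5, show Grade 5 on its own row, and state that each participant is counted once, by maximum grade. Use the same grade cut as the overall AE tables so that subgroup and overall results can be compared.

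The cost is a change of phrase, one sentence on counting and one more table row. No new data are needed, because Grade 5 is already on the recording scale. The small downside is that the main AE tables are redacted here, so the sponsor must check their grade cut and may need to align the two.
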